## **5.6 Protocol Deviations**

Protocol deviations will be recorded by the site separately from the clinical database. IQVIA/Shire will classify major and minor protocol deviations per the agreed protocol deviation management plan. The Shire study team will review the protocol deviations and their classification throughout the study and before treatment unblinding and database lock. Decisions of the review will include the accuracy of major and minor protocol deviations categorization based on the clinical and medical team review of the clinical database. Confirmed major and minor protocol deviations will be documented in the Protocol Deviation tracker for the study. Major/minor protocol deviations will be listed for the Safety Set.

## **6. EFFICACY ANALYSES**

All raw (actual) efficacy endpoints will be listed for the Safety Set. The efficacy endpoints described in Section 2.3 will not be derived. The following efficacy dataset listings will be presented for lung density CT scan, pulmonary function (spirometry and lung volumes), 6MWT, MMRC dyspnea scale, BODE index, SGRQ-C, and SF-36.

### **6.1 Analyses of Primary Efficacy Endpoints**

The primary efficacy endpoint is rate of change in lung density (15th percentile of the lung density measurements [PD15] as assessed by CT densitometry) that is measured every 6 months. The overall sample size at the termination of the study was small. The analysis and summarization for rate of change in lung density will not be presented.

### **6.2 Secondary Efficacy Endpoint**

Not Applicable

### **6.3 Multiplicity Adjustment**

Not Applicable

### **6.4 Analyses of Exploratory Endpoint(s)**

Not Applicable

### **6.5 Subgroup Analyses**

Not Applicable

## **7. SAFETY ANALYSIS**

The safety analysis will be performed using the Safety Set. Safety variables include AEs, clinical laboratory variables, vital signs, and electrocardiogram (ECG) variables.

## 7.1 Adverse Events

Adverse events will be coded using MedDRA Version 21.0 or newer.

An AE (classified by preferred term) that occurs during the double-blind evaluation phase will be considered a treatment-emergent AE (TEAE) if it has a start date on or after the first dose of double-blind IP or if it has a start date before the date of the first dose of double-blind IP, but increases in severity on or after the date of the first dose of double-blind IP.

An overall summary of the number of subjects with TEAEs as well as the number of events by treatment group and overall will be presented. The table will also be summarized by any TEAEs during or within 72 hours following the end of the IP infusion. The table will include the number and percentage of subjects with any TEAEs, serious TEAEs, severe TEAEs, TEAEs related to IP and TEAEs leading to discontinuation of IP.

All AEs will be listed for the Safety Set.

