## 1. INTRODUCTION

This is a pilot study to assess the safety and efficacy of alpha1-proteinase inhibitor (A1PI) augmentation therapy in subjects with emphysema/chronic obstructive pulmonary disease (COPD) associated with severe congenital A1PI deficiency with endogenous plasma A1PI level of  $< 8 \mu\text{M}$  and documented A1PI genotypes of Pi\*Z/Z, Pi\*Z/null, Pi\*Malton/Z, Pi\*Null/Null, or other rare genotypes (except PI\*MS, PI\*MZ, or PI\*SZ). Intravenous (IV) ARALAST NP and GLASSIA augmentation therapy administered as an IV infusion at 60 mg/kg body weight (BW)/week or 120 mg/kg BW/week was to be compared to placebo. The protective effects of ARALAST NP and GLASSIA were expected to be reflected in the preservation of lung parenchyma, as measured by computerized tomography (CT) lung densitometry. In addition, the functional integrity of lung parenchyma was to be evaluated by measurements of selected respiratory physiology variables.

ARALAST NP and GLASSIA were approved by the Food and Drug Administration (FDA) for chronic augmentation and maintenance therapy in adults with clinically evident emphysema due to severe congenital deficiency of A1PI. The results of this study, along with available scientific data, may be used to design an adequately powered Stage 2 clinical study.

On 24 JUL 2018, Shire prematurely terminated the entire study following the unanimous vote by the Data Monitoring Committee (DMC) on 25 June 2018. The decision was based on the very low number of randomizations, slow rate of enrolling participants relative to the enrollment targets, and the difficulties of enrolling patients who would have to agree to be potentially randomized to receive placebo. Continuation of the trial would potentially place participants at increased risk due to the study procedures (including but not limited to radiation from the chest CT scan), not receiving active drug and inconvenience of study visits.

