## 2.3 Endpoints

The endpoints provided are from the protocol amendment 11. However, due to the study being prematurely terminated, the derived endpoints will not be presented in the data listing and analysis will not be performed using the endpoints.

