### 2.3.4 Safety Endpoints

1. Number and rate of related and unrelated serious and non-serious AEs
2. Number and rate of temporally related serious and non-serious AEs (ie, AEs which began during or within 72 hours following the end of IP infusion)
3. Number and rate of suspected adverse reactions plus adverse reactions
4. Number (proportion) of infusions for which the infusion rate was reduced and/or the infusion interrupted or stopped due to AEs
5. Number (proportion) of subjects who develop anti-A1PI antibodies following treatment with ARALAST NP or GLASSIA

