### 3.1.1 Figure Study Flow Chart

Approximately 138 adult subjects diagnosed with severe congenital A1PI deficiency and emphysema/COPD were to be enrolled to meet the target of 110 randomized subjects, assuming a 20% screen failure rate. Subjects could be either A1PI naïve (untreated), previously treated, or currently receiving A1PI augmentation therapy at the time of study entry.

Subjects who were receiving or had been treated within 4 weeks of screening, with A1PI augmentation therapy would be required to have their pre-study A1PI augmentation therapy discontinued and undergo a washout period of at least 4 weeks for A1PI levels to return to endogenous (pre-augmentation) levels. Plasma A1PI levels were to be assessed to verify adequacy of A1PI washout and to confirm diagnosis of A1PI deficiency. All other screening procedures were to be performed prior to the completion of the washout period.

Subjects meeting eligibility criteria will undergo baseline assessments prior to the first dose of IP. Subjects were to be randomly assigned to receive one of the five treatments groups for 24 months (104 weeks). The IP was to be administered via weekly IV infusions. The first IP infusion was to be administered at the study site. At the investigator's discretion, subsequent infusions could be administered at the study site or at another suitable location (ie, the subject's home) by a qualified healthcare professional, except for those that occurred during the same week as the clinic visits.

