### **5.5 Exposure to Investigational Product**

Exposure to IP for the Safety Set will be summarized in terms of number of infusions, duration of exposure, and average weekly dose. The duration of exposure is calculated as the number of days from the date of first dose of IP taken to the date of the last dose of IP taken, inclusively. The average weekly dose is calculated as (total volume administered/ total planned volume) \* actual dose (either 60 mg or 120 mg). For placebo, the actual dose would be 0. The average weekly dose is the average of the weekly doses for each subject.

Descriptive statistics (n, mean, standard deviation, minimum, median, and maximum) will be presented to describe the exposure to IP by treatment group and overall.

The number and proportion of subjects with at least one infusion rate change, one infusion rate interruption, or one infusion stopped will be summarized by treatment and overall.

The details of exposure to IP will be listed for the Safety Set.

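### The one adverse event table kept after early termination has no exposure denominator, so in very small arms chance differences in follow-up can make equal event rates look unequal

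*SAP*

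**What the plan says.** Section 7.1 of the SAP specifies a single table by treatment group and overall: "An overall summary of the number of subjects with TEAEs as well as the number of events by treatment group and overall will be presented". Its rows are subject-based: "The table will include the number and percentage of subjects with any TEAEs, serious TEAEs, severe TEAEs, TEAEs related to IP", plus events leading to discontinuation. The infusion-related rows follow the same format: "The table will also be summarized by any TEAEs during or within 72 hours following the end of the IP infusion". No row is divided by time at risk or by infusions given.

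Section 3.1.1 planned 24 months (104 weeks) of weekly infusions for every subject. Section 1 records what happened: "On 24 JUL 2018, Shire prematurely terminated the entire study following the unanimous vote by the Data Monitoring Committee (DMC) on 25 June 2018". Sections 1 and 12 both give very few randomizations and slow enrolment as reasons.

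Section 5.5 handles exposure in a separate table, also by treatment group: "Exposure to IP for the Safety Set will be summarized in terms of number of infusions, duration of exposure, and average weekly dose". Its duration runs from first to last dose, inclusive. Section 12 limits the summary tables to disposition, demographics, exposure and overall adverse events.

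**The concern.** With a fixed 104 weeks per subject, percentages of subjects with an event would have had a roughly common time base in every arm. A stop on one calendar date removes that. A subject still on treatment at the stop has follow-up set by the date of entry. The more follow-up an arm has, the more events it shows, and the more of its subjects have at least one, even if the underlying rate is the same everywhere.

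This table is the only adverse event summary left, and Section 2.1.2.2 keeps safety at both dose levels as an objective. Readers will look across the five columns. In arms of a few subjects, differences in entry date alone can imitate or hide a difference between doses or products.

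**Working it through.** **Plan's own figures.** The SAP states no event rate, no final number of subjects and no follow-up by arm, so there is no adverse event figure to reproduce. The planned allocation does reproduce: 110 / (1+1+1+1+1.5) = 20 per active arm, and 1.5 × 20 = 30 on placebo, as in Section 3.2.

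**Step 1: effect of follow-up at a constant rate.** Event rates here are assumptions. P(at least one event) = 1 − exp(−rate × weeks/52).

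| Assumed rate per subject-year | 13 weeks | 26 weeks | 52 weeks | 104 weeks |
|---|---|---|---|---|
| 1 | 22.1% | 39.3% | 63.2% | 86.5% |
| 3 | 52.8% | 77.7% | 95.0% | 99.8% |

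Expected events per subject = rate × weeks/52. At 1 per year that is 0.5 at 26 weeks and 2.0 at 104. At high rates the percentages saturate but the counts do not: at 4 per year, 52 against 104 weeks gives 98.2% against 100.0% of subjects, but 4 against 8 events each. A smaller gap matters less: 45 against 60 weeks at 1 per year gives 57.9% against 68.5%.

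**Step 2: how far arms could differ by chance.** Assume follow-up at the stop is uniform on 1 to 104 weeks, independently of arm. In simulation, total exposure in two equal arms differs by a factor of 1.5 or more in about 51% of draws with 2 subjects per arm, 34% with 4 and 17% with 8. Across five arms of 4, the median ratio of largest to smallest total is about 2.0.

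Keeping the 1:1:1:1:1.5 ratio (placebo size rounded up) and 1 event per subject-year:

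| Subjects per active arm | Median longest/shortest mean follow-up | Median spread in expected percentage with an event |
|---|---|---|
| 2 | 2.6 | 36 points |
| 3 | 2.1 | 30 points |
| 5 | 1.8 | 23 points |
| 20 (as planned) | 1.3 | 12 points |

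**Step 3: allocation.** With equal rates and equal follow-up, placebo expects 30/20 = 1.5 times the events of each active arm. Raw event counts therefore favour the active arms by design; percentages do not have this fault.

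**Step 4: what a denominator buys.** Two identical arms of 4, follow-up as in step 2, Poisson events. The table gives the share of draws in which the arms differ 1.5-fold or more.

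| True rate per subject-year | Raw counts | Events per subject-year |
|---|---|---|
| 1 | 69% | 60% |
| 3 | 52% | 35% |
| 6 | 44% | 19% |

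At 1 per year, most of the spurious difference is small-number noise: raw counts differ that much in 64% of draws even with exactly equal exposure. At higher rates the denominator removes a large part of it.

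**Step 5: which denominator.** Section 7.1 starts counting at the first dose and gives no end date. Section 3.1.1 follows subjects for one week after treatment. For a subject with one infusion, the Section 5.5 duration is 1 day, while events could be counted over about 1 + 7 = 8 days. The Section 5.5 duration therefore does not match the numerator.

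**The case against.** Four points weigh against the concern, and each stands in part.

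- **The table is descriptive.** Section 7.1 plans no test or contrast, and Section 3.4 says the study is not powered for hypothesis tests. A reader might infer that the SAP formally compares the five arms on crude percentages; it does not. The columns still stand side by side, with no warning that they are not exposure-adjusted.
- **Unequal follow-up between arms is not documented.** A reader might infer that termination biased the arms. Under concurrent randomization, one stopping date gives every arm the same expected administrative follow-up. What remains is possible chance imbalance, whose actual size the SAP does not show.
- **Exposure is reported by arm.** From n and mean in the Section 5.5 table, a reader can form total infusions and an approximate subject-time, and hence crude rates. Exposure and adverse events are also listed by subject. The gap is therefore mainly one of layout, but the SAP neither makes the link nor tells the reader to.
- **The rate endpoints were set aside.** Section 2.3.4 names "Number and rate of related and unrelated serious and non-serious AEs", and a reader might infer that Section 7.1 fails its own endpoint. Section 2.3 says otherwise: "the derived endpoints will not be presented in the data listing and analysis will not be performed using the endpoints". Section 12 repeats this, and Section 2.3.4 gives its rate no denominator. The point must rest on the retained table alone.

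It is also true that rates from a handful of subjects are imprecise, as step 4 shows.

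**Conclusion.** The point holds as a minor-to-moderate weakness of a descriptive table. Counts, percentages and raw events without a time base can make arms with equal event rates look different when follow-up varies and arms are very small; raw event counts are also distorted by the allocation ratio.

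The size is illustrative. It rests on an assumed constant event rate, follow-up assumed uniform on 1 to 104 weeks, and assumed arm sizes. Under those assumptions the median spread in expected percentages is 23 to 36 points with 5 down to 2 subjects per active arm. The gain from a rate is modest at 1 event per subject-year and clear at 3 or 6.

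The documents do not show that the arms did differ in follow-up, that any safety conclusion is wrong, or that the SAP breaches an endpoint still in force.

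**What to change.** In Section 7.1:

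- Keep the counts and percentages.
- Print total subject-years at risk and total infusions given in each column header.
- Add events per subject-year, and for the 72-hour rows events per infusion.
- Define time at risk over the window in which treatment-emergent events are counted (first dose to the end of safety follow-up or last contact), state that end point in the definition, and do not substitute the Section 5.5 duration.
- Add a footnote that percentages and raw counts are not exposure-adjusted, and that rates in arms this small are imprecise and descriptive only.

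The SAP need not direct that arms be compared on these rates; that would add an inference it does not plan.

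The cost is a few sentences and table entries, using infusion counts already summarized and one further derived time variable. The downsides are imprecise rates and a summary that assumes a roughly constant event rate over time.

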## 7.2 Clinical Laboratory Data

Clinical laboratory values will be listed for the Safety Set for the following clinical laboratory variables:

Hematology	Hemoglobin, hematocrit, erythrocytes (ie, red blood cell count), leukocytes (ie, white blood cell count) with differential (ie, basophils, eosinophils, lymphocytes, monocytes, neutrophils), and platelet count.
Biochemistry	Sodium, potassium, chloride, bicarbonate, phosphorus, total protein, albumin, alanine aminotransferase, aspartate aminotransferase, alkaline phosphatase, lactate dehydrogenase, gamma-glutamyl-transferase, creatine phosphokinase, bilirubin (direct and total), blood urea nitrogen, uric acid, creatinine, and glucose.
Urinalysis	Color, specific gravity, pH, protein, glucose, ketones, bilirubin, urobilinogen, blood, nitrate, leukocyte esterase, and microscopic examination (red blood cell, white blood cell, bacteria, casts). Only recorded at screening.
Other	Cotinine and pregnancy test.

### **7.3 Vital Signs**

All vital signs data (e.g., systolic and diastolic blood pressure, pulse rate, respiratory rate, body weight, body temperature, and BMI) will be listed for the Safety Set.

### **7.4 Electrocardiogram (ECG)**

All ECG data (e.g., heart rate, PR interval, QRS interval, QT interval, and QTc interval) will be listed for the Safety Set.

### **7.5 Other Safety Data**

If available, the number of subjects with anti-A1PI antibodies will be summarized by treatment group and overall over the schedule time point of collections. The immunogenicity data will be listed for the Safety Set.

## **8. PHARMACOKINETIC ANALYSIS**

### **8.1 Drug Concentration**

All antigenic and functional A1PI levels will be listed for the Safety Set.

## **9. DATA MONITORING COMMITTEE**

This study was monitored by a DMC. The DMC is a group of individuals with pertinent expertise that reviews on a regular basis accumulating data from an ongoing clinical study. For this study, the DMC was composed of recognized experts in the field of alpha1-proteinase inhibitor deficiency and COPD clinical care and research who were not actively recruiting subjects.

The DMC were responsible for monitoring the safety of the study participants including periodic review of serious AEs, AEs, and any relevant information that may have had an impact on the safety of the participants or the ethics of the trial. Based on data review, the DMC could make a recommendation to continue the study as is, temporarily suspend the study, or terminate the study based on pre-defined criteria such as unacceptable toxicities or lack of treatment benefits. The membership, responsibilities, interactions, and operations of the DMC in providing oversight of the study, as well as criteria for DMC recommendations, are detailed in the DMC Charter.

## **10. DATA HANDLING CONVENTIONS**

### **10.1 General Data Reporting Conventions**

Continuous variables will be summarized using the following descriptive statistics: n, mean, median, standard deviation, minimum, maximum. Categorical variables will be summarized by the number of subjects (n) and the percent of subjects in each category.

Refer to the Shire TFL Standards for rules on the number of decimal places to present.

### **10.2 Definition of Baseline**

Not Applicable

### **10.3 Definition of Visit Windows**

Not Applicable

### **10.4 Derived Efficacy Endpoints**

Not Applicable

### **10.5 Repeated or Unscheduled Assessments of Safety Parameters**

Not Applicable

### **10.6 Handling of Missing, Unused, and Spurious Data**

#### **10.6.1 Missing Date of Investigational Product**

When the date of the last dose of IP is missing for a subject in the Safety Set, all efforts should be made to obtain the date from the investigator. If it is still missing after all efforts, then the last visit date when IP was returned will be used in the calculation of treatment duration.

#### **10.6.2 Missing Date Information for Concomitant Medications, Non-Drug Therapies, and Procedures**

The missing dates for concomitant medications, non-drug therapies, and procedures will not be imputed. The dates will be presented “as is” in the data listings.

#### **10.6.3 Missing Date Information for Adverse Events**

For AEs with partial start dates, non-missing date parts will be used to determine if the AE is treatment-emergent or not. If a determination cannot be made using the non-missing date parts as to when the AE occurred relative to study drug administration, e.g.

AE start year and month are the same as the year and month of the first dose of IP, then the AE will be classified as treatment-emergent.

To facilitate categorization of AEs as treatment-emergent, imputation of dates can be used. For AEs, the default is to only impute incomplete (i.e., partially missing) start dates. Incomplete stop dates may also be imputed when calculation of the duration of an AE is required per the protocol. If imputation of an incomplete stop date is required, and both the start date and the stop date are incomplete for a subject, impute the start date first.

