#### **10.6.3.1 Incomplete Start Date**

The following rules will be applied to impute the missing numerical fields. If the stop date is complete and the imputed start date is after the stop date, then the start date will be imputed using the stop date.

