##### **10.6.3.1.1 Missing Day and Month**

- If the year of the incomplete start date is the same as the year of the date of the first dose of IP, then the day and month of the date of the first dose of IP will be assigned to the missing fields
- If the year of the incomplete start date is before the year of the date of the first dose of IP, then December 31 will be assigned to the missing fields
- If the year of the incomplete start date is after the year of the date of the first dose of IP, then 01 January will be assigned to the missing fields.

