### **10.6.3.2 Incomplete Stop Date**

The following rules will be applied to impute the missing numerical fields. If the date of the last dose of IP is missing, then replace it with the last visit date. If the imputed stop date is before the start date (imputed or non-imputed start date), then the imputed stop date will be equal to the start date.

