14. APPENDICES

14.1 Schedule of Study Procedures and Assessments

Table 14-1 Schedule of Study Procedures and Assessments													
Procedure/ Assessment	Scr (Max 6 Weeks)	Treatment Period										Study Completion	Early Termination
		Week 1	Week 4 (± 2 Days)	Week 13 (± 2 Days)	Week 26 (± 2 Days)	Week 39 (± 2 Days)	Week 52 (± 2 Days)	Week 65 (± 2 Days)	Week 78 (± 2 Days)	Week 91 (± 2 Days)	Week 104 (± 2 Days)	Week 105 (± 2 Days)	1 Weeks (± 2 Days) Post-Last Infusion
Informed Consent a	X												
Eligibility Determination	X												
Demographics	X												
Medical, Medication, and Non-Drug Therapy History	X												
Smoking history	X												
Body Height	X												
Body Weight b	X	X	X	X	X	X	X	X	X	X	X	X	X c
BMI	X	X			X		X		X		X		X c
Physical Exam	X	X	X	X	X	X	X	X	X	X	X	X	X
Vital Signs d	X	X	X	X	X	X	X	X	X	X	X	X	X
12-Lead ECG	X e										X		
Chest X-Ray/CT	X												
Pulmonary function tests f	X	X g,h			X g		X g		X g		X g		X c
Lung density CT scan i		X g,h			X g,i		X g,i		X g,i		X g,i		X c

Table 14-1 Schedule of Study Procedures and Assessments													
Procedure/ Assessment	Scr (Max 6 Weeks)	Treatment Period										Study Completion	Early Termination
		Week 1	Week 4 (± 2 Days)	Week 13 (± 2 Days)	Week 26 (± 2 Days)	Week 39 (± 2 Days)	Week 52 (± 2 Days)	Week 65 (± 2 Days)	Week 78 (± 2 Days)	Week 91 (± 2 Days)	Week 104 (± 2 Days)	Week 105 (± 2 Days)	1 Weeks (± 2 Days) Post-Last Infusion
6MWT		X g,h			X g		X g		X g		X g		X c
MMRC dyspnea scale		X g,h			X g		X g		X g		X g		X c
BODE Index		X g,h			X g		X g		X g		X g		X c
HRQoL (SGRQ-C and SF-36)		X g,h			X		X		X		X		X c
Clinical Laboratory Assessments j	X	X g,h	X	X	X	X	X	X	X	X	X	X	X
COPD Exacerbations	X	Weekly (Weeks 1 – 104)										X	X
IP Treatment k		Weekly (Weeks 1 – 104)											
Telephone follow-up l		Weekly (Weeks 1 – 104)											
Concomitant Medications and non-drug therapies	X	Weekly (Weeks 1 – 104)										X	X
Adverse Events	X	Weekly (Weeks 1 – 104)										X	X

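### An AE with only a start year and a partial stop date before the first-dose month is imputed to the first-dose date and counts as a TEAE, and the SAP does not say whether 10.6.3 or 10.6.3.1 prevails

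*SAP*

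**What the plan says.** Section 7.1 sets the start-date test for an AE arising in the double-blind phase: it "will be considered a treatment-emergent AE (TEAE) if it has a start date on or after the first dose of double-blind IP"; worsening on or after first dose also qualifies. TEAEs during or within 72 hours of an infusion are summarised as well.

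Section 10.6.3 gives a first route for incomplete dates: "For AEs with partial start dates, non-missing date parts will be used to determine if the AE is treatment-emergent or not". The default to treatment-emergent then applies under this condition: "If a determination cannot be made using the non-missing date parts as to when the AE occurred relative to study drug administration". The one example given concerns the start date only: "AE start year and month are the same as the year and month of the first dose of IP, then the AE will be classified"; the class assigned there is treatment-emergent. The section then allows imputation for the same purpose, without making it mandatory. By default only start dates are imputed. Stop dates may be imputed when an AE duration is needed, and if both dates are incomplete the start is imputed first.

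Section 10.6.3.1 is the second route, and its rules are worded as binding. Under 10.6.3.1.1, when day and month are missing and the year is that of first dose, "then the day and month of the date of the first dose of IP will be assigned to the missing fields". Section 10.6.3.1.2 sends a start with only the month missing to the same rule. The safeguard, which resets the start from the stop date, opens with this condition: "If the stop date is complete and the imputed start date is after the stop date".

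Section 10.6.3.2 adds that if an imputed stop falls before the start, "then the imputed stop date will be equal to the start date".

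Table 14-1 collects AEs from screening, which may last up to 6 weeks before Week 1.

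**The concern.** Because AEs are collected during screening, some may begin and end before the first infusion. Defaulting to treatment-emergent is sensible when the timing is unknown. It is not sensible when the recorded stop date, even a partial one, settles it.

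The safeguard in 10.6.3.1 ignores partial stop dates. A stop month that precedes the first-dose month therefore has no influence on the imputed start, and an event that was over before dosing can be dated to the first-infusion day.

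The two routes also draw on different information, and nothing ranks them. Two competent programmers could classify the same event differently.

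The overall AE summary is one of the four kinds of summary table that Sections 1 and 12 retain, so the classification reaches a reported output. A start placed on the first-infusion day can also reach the 72-hour row. The SAP does not say whether that row is derived from dates or from a field on the eCRF.

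**Working it through.** The plan gives no figure to reproduce; the check traces the rules.

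**Inputs.** The TEAE test is from Section 7.1, the default from 10.6.3, start imputation from 10.6.3.1.1 to 10.6.3.1.3, the complete-stop safeguard from 10.6.3.1, and stop imputation from 10.6.3.2. Illustrative dates, not in the SAP: first dose 15 Jun 2017, last dose 14 Jun 2018.

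**Worked cases**

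| Case | Recorded start | Recorded stop | Known to have ended before first dose? | 10.6.3, start parts only | 10.6.3, all date parts | 10.6.3.1: imputed start and result |
|---|---|---|---|---|---|---|
| A | Jun 2017 | 10 Jun 2017 | Yes | TEAE | Not TEAE | 10 Jun 2017, not TEAE |
| B | 2017 | 20 May 2017 | Yes | TEAE | Not TEAE | 20 May 2017, not TEAE |
| C | 2017 | May 2017 | Yes | TEAE | Not TEAE | 15 Jun 2017, TEAE |
| D | Jun 2017 | Jun 2017 | No | TEAE | TEAE | 15 Jun 2017, TEAE |

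**Case C, step by step.**
1. The start year equals the first-dose year, so 10.6.3.1.1 sets the start to 15 Jun 2017.
2. The stop date lacks its day, so the safeguard does not apply.
3. The imputed start is on the first-dose date, so the Section 7.1 start-date test is met. The recorded stop of May 2017 is nevertheless before any IP.
4. Only if a duration were needed would the stop be imputed, to 31 May 2017, and then moved to 15 Jun 2017 under 10.6.3.2. Step 3 does not depend on this.

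**How wide is the pattern?** All combinations of start and stop day within the 42 days before first dose were enumerated for every first-dose date in 2017: 365 × (42 × 43 / 2) = 365 × 903 = 329,595 combinations. Each was examined with the start recorded as year and month, or as year only.

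- Complete stop date: 2 × 329,595 = 659,190 patterns, and 10.6.3.1 produced no false TEAE. Section 10.6.3 read on start parts alone disagreed in 304,010 (year-only start) + 56,354 (start with month) = 360,364 of them.
- Stop with month and year, in a month before the first-dose month: 154,910 patterns for each type of start. With the start month recorded, 10.6.3.1 gave no false TEAE. With the start year only, it gave a false TEAE in 139,620, which are all those whose start year is the first-dose year. In the other 15,290 the start year was earlier, and the result was correct.

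These are counts of date patterns. They are not event rates, because the SAP says nothing about how often dates are partial.

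**Precedence.** If 10.6.3 uses start parts only, it disagrees with 10.6.3.1 in cases A and B, and both routes are wrong in case C. If it uses all recorded parts, A and B agree and the disagreement moves to case C. Neither reading makes both routes right in all of A, B and C.

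**Effect of one event.** One misclassified subject with no other TEAE adds 1/n to an arm's proportion with any TEAE. At the planned arm sizes this is 1/30 = 3.3 percentage points (placebo) or 1/20 = 5 points (each active arm). In an assumed arm of 5 it is 1/5 = 20 points. The SAP gives no actual arm sizes.

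**The case against.** The strongest reply is that Section 10.6.3 does not confine itself to start-date parts. Its example is only an example, and a stop date before first dose does settle the timing, so the default is never reached. Section 7.1 supports this by requiring the AE to occur in the double-blind phase. On that reading cases A and B are classified correctly by both sections. This stands as a reasonable reading, but the text does not state it. It also leaves case C, where 10.6.3.1 still dates the event to first dose. The phase condition shows the intent, yet a program judges phase from dates, and the imputed date places the event in the phase.

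Imputation is also optional under 10.6.3. That is true, but 10.6.3.1 words its rules as binding, which is why precedence needs stating.

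Three stronger readings are tempting, and the SAP does not support them:
- A reader might infer that any AE known to have ended before first dose becomes a TEAE dated to the first infusion. With a complete stop date, 10.6.3.1 never does this.
- A reader might infer that recorded stop months will be overwritten in the outputs. Stop dates are imputed only when a duration is required, no planned table needs one, and listings show values as recorded.
- A reader might size the problem from the share of screening days falling in the first-dose month. That share concerns starts lacking only the day. There the safeguard works if the stop is complete, and a stop recorded only as that same month does not show that the AE ended before dosing.

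Finally, the report is abbreviated and descriptive, the error runs towards over-counting, and every AE is listed for the Safety Set. This limits the consequence but does not make the rule right.

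**Conclusion.** The point holds in a narrow form. Applied literally, 10.6.3.1 gives a wrong result for one pattern: the start month is unknown, the start year is that of first dose, and the partial stop date falls in a month before the first-dose month. Such an event meets the start-date test for a TEAE and can enter the 72-hour row.

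The lack of a stated order between 10.6.3 and 10.6.3.1 is a separate ambiguity. Its effect on AEs with complete stop dates depends on reading 10.6.3 as limited to start parts.

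The number of affected events cannot be determined from the SAP and is likely small. The percentage-point effects shown assume one such subject with no other TEAE; the arm of 5 is an assumption. This is a modest specification flaw, worth correcting because the remedy is so cheap.

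**What to change.** 1. In Section 10.6.3, state that an AE whose complete or partial stop date shows it ended before the first dose of IP is not treatment-emergent, whatever is missing from the start date, and that this overrides the default.
2. In Section 10.6.3.1, extend the check to partial stop dates by capping the imputed start at the latest date consistent with the recorded stop parts.

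With these changes cases A, B and C become non-treatment-emergent by both routes; in case C the start is capped at 31 May 2017. Case D, which is truly ambiguous, stays a TEAE.

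Section 10.6.3.2 needs changing only if AE durations are calculated. In that event an imputed stop should not be moved beyond its recorded month and year; the imputed start should be corrected instead.

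The cost is two sentences of SAP text and a few lines of programming. The TEAE count may fall slightly, and all AEs remain in the listing.
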